#### Power calculation

The results from this study will be used to inform a power calculation to determine the sample size for a larger trial investigating the outcome measures described in Section 6.2. Specific statistical support will be sought within the Department of Cardiovascular Sciences to carry out this power calculation using the outcome data from this study.

## 11.2 The Number of Participants

60 participants will be required to complete the programme, in three sub-groups of twenty (healthy older adults, AzD and MCI). This does not include participants who did not have adequate bilateral TCD windows, which has been listed in section 7.3 as an exclusion criterion. Authors generally agree that recruiting between 24 and 50 participants for a feasibility study is adequate and therefore the planned target of 60 participants is sufficiently large enough whilst giving a margin for drop-outs and loss to follow-up (41, 42). Given the primary aim of this study is feasibility, a formal power calculation has not been performed.

For the qualitative arm, participants will be recruited as a sub-set of those who were enrolled into the training arm of the trial. Both participants who did and did not complete the training programme will be invited for interview or focus group to better understand any issues that arose during the programme, reasons for non-adherence, or premature withdrawal. The sample size will therefore be determined by the number who were randomised to the treatment arm and are willing to return for interview or focus group. At the point at which responses to interview questions become saturated, no further participants will be recruited to the qualitative arm.

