## 2. SYNOPSIS

Study Title	The Cognition and Flow Study: The Effects of Brain Training on Brain Blood Flow
Internal ref. no.	0677
Trial Design	Feasibility Randomised Controlled Trial
Trial Participants	Healthy older adults, adults with mild cognitive impairment (undifferentiated), adults with mild to moderate Alzheimer's disease, adults 12 months post-ischaemic stroke.
Planned Sample Size	80 participants in total, 20 participants in each of the four sub-groups.
Follow-up duration	Three to six months
Planned Trial Period	12 -18 months
Primary Objective	The primary objective of this study is to determine the ability to carry out (feasibility) of a large scale randomised controlled trial (RCT) of cognitive training (CT) in healthy older adults (HC), and people with Alzheimer's disease (AzD), mild cognitive impairment (MCI), and people post-ischaemic stroke.
Secondary Objectives	Are there any clinical benefits of a CT program in patients with dementia and any difference between groups (MCI/AzD/healthy older adults/post-ischaemic stroke) in ability to carry out everyday activities, memory, mood, and quality of life outcomes?
Primary Endpoints	
 
1) Percentage of participants successfully recruited
 
2) Percentage of participants able to successfully complete CT program and complete all assessments
 
3) Percentage of participants with full bilateral data for CBFv
 
4) Feasibility of randomisation to waiting list control
 

Secondary Endpoints	
 
1) Change in cognition score as detected by the Addenbrooke's cognitive examination (ACE-III)
 
2) Change in functional status - Lawton Instrumental Activities of Daily Living (IADL)
 

	
3) Change in mood – Geriatric Depression Scale (GDS-15)
 
4) Change in quality of life measure – Dementia Quality of Life Measure (DEMQOL)
 
5) Change in task activation increase in CBFv from baseline

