**5. OBJECTIVES**

### 5.1 Primary Objectives

The primary objective of this study is to determine the ability to carry out (feasibility) a large scale RCT of CT in healthy older adults, and people with AzD and MCI.

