### 5.2 Secondary Objectives

- 1) Are there any clinical benefits of a brain training program in patients with dementia and any difference between groups (MCI/AzD/healthy older adults/post-ischaemic stroke) in ability to carry out everyday activities, memory, mood, and quality of life outcomes?
- 2) Are there any changes in blood flow responses to cognitive tasks using TCD before and after brain training?
- 3) Are there any brain blood flow markers that can be used to predict who will benefit from brain training, and in which memory areas to generate a personalised training plan for individual patients?

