## 6. STUDY DESIGN

### 6.1 Summary of Trial Design

This is a prospective, feasibility, RCT of CT in healthy older adults, and adults with AzD, MCI, or post-ischaemic stroke. This trial is un-blinded, due to the nature of the intervention. The expected duration of participation per individual is three to six months. Initially, participants will be approached by a member of the clinical care team or research support staff, who will screen and identify eligible participants. Study specific information will then be provided by the researcher. Following this, participants will undergo informed consent. Each participant will have two visits (initial and follow-up assessment). After the first visit, participants will be randomised to control or intervention (CT), and will complete an 8-12 week CT program, if selected for the intervention group. Participants will be randomised using Sealed Envelope ©, an online, commercially available randomisation tool. At the end of the trial, participants will be given the option to participate in a qualitative study by semi-structured interviews or focus group. A flow chart for this process can be seen in Appendix A.

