#### **Recruitment**

A broad recruitment strategy has been developed to ensure this project can recruit to target (total 60 participants, 20 healthy older adults, 20 MCI and 20 AzD). This will encompass memory and geriatric clinics, GP surgeries, and community groups. This recruitment strategy and rate has been based on a recent pilot study undertaken in the department where 55 participants were recruited over a period of 6 months.

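### Sections 11.2 and 14.1 still give 60 participants in three groups where the synopsis plans 80 in four; section 5.1 and the baseline comparison list in section 11.1 also leave out the post-stroke group

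*Combined protocol and SAP*

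**What the plan says.** **Total and number of groups.** The synopsis plans "80 participants in total, 20 participants in each of the four sub-groups". Section 11.2 says "60 participants will be required to complete the programme, in three sub-groups of twenty (healthy older adults, AzD and MCI", and defends that figure by saying that "the planned target of 60 participants is sufficiently large enough whilst giving a margin for drop-outs and loss to follow-up". The recruitment paragraph of section 14.1 aims to "recruit to target (total 60 participants, 20 healthy older adults, 20 MCI and 20 AzD".

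**Who is in the trial.** Section 6.1 states: "This is a prospective, feasibility, RCT of CT in healthy older adults, and adults with AzD, MCI, or post-ischaemic stroke". Section 5.2 asks about "any difference between groups (MCI/AzD/healthy older adults/post-ischaemic stroke". Post-ischaemic stroke is also one of the four populations in section 7.1, has its own inclusion criterion in section 7.2, and has its own recruitment paragraph in section 8.1, which gives it the same study procedures as the other groups.

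**Primary objective.** The synopsis ends its list of populations with "mild cognitive impairment (MCI), and people post-ischaemic stroke". Section 5.1 gives the same objective as "a large scale RCT of CT in healthy older adults, and people with AzD and MCI" and does not mention stroke.

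**Analysis text.** Under Feasibility and Baseline Demographics, section 11.1 compares the arms within each population and names the populations as healthy controls, AzD and MCI. Under Outcome Data, the two-way ANOVA refers to population group without listing any.

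**First primary endpoint.** Recruitment is a percentage in the synopsis, with no denominator, and a number in section 6.2.

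**The concern.** All of these passages are current text. The amendment history records that the post-stroke group was added in version 5. That suggests how the mismatch arose, but the conflict does not depend on it.

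Section 11.2 is where a reader looks for the sample size, and there both the total and the number of groups disagree with the synopsis. Recruitment is the first primary endpoint of a feasibility trial, so the intended total ought to be unambiguous. Three practical matters also depend on it: how many people must be assessed for Doppler windows, how long recruitment should take, and which participant is the last one for the definition of the end of the trial in section 8.8. The justification in section 11.2 and the recruitment-rate argument in section 14.1 are both written for 60 people in three groups. Outside the synopsis, no section gives the post-stroke group a sample size.

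**Working it through.** **Reproducing the two totals.**
- Section 11.2 and section 14.1: 3 groups × 20 = 60.
- Synopsis: 4 groups × 20 = 80.

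Each total is correct for its own list of groups. They differ by 80 − 60 = 20, exactly the post-stroke group.

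**Can one total be derived from the other?**
- *Window failure.* Section 8.4 expects about 20–25% of potential participants to lack adequate bilateral windows. 60 / (1 − 0.25) = 80, which looks like a reconciliation. It is a coincidence: the synopsis builds 80 as four groups of 20, and section 11.2 says its count already leaves out people without windows.
- *Completers against enrolled.* The opening sentence of section 11.2 can be read as counting completers. The same paragraph then calls 60 the target and says it leaves room for drop-outs, and section 14.1 treats 60 as the number to recruit. Neither reading explains why one list has three groups and the other four.

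**Assessment load.** Number to assess = number to enter / (1 − window failure rate), using the 20–25% in section 8.4 and assuming it applies equally to the stroke group.

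| To enter | 20% failure | 25% failure |
|---|---|---|
| 60 | 60 / 0.80 = 75 | 60 / 0.75 = 80 |
| 80 | 80 / 0.80 = 100 | 80 / 0.75 = 106.7, so 107 |

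**Recruitment time.** Section 14.1 bases its rate on a pilot that recruited 55 people in 6 months, or 55 / 6 = 9.17 per month.
- 60 / 9.17 = 6.5 months.
- 80 / 9.17 = 8.7 months.

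This assumes that the pilot rate carries over to all groups. The channels named beside it in section 14.1 are memory and geriatric clinics, GP surgeries and community groups; the stroke wards and stroke clinics of section 8.1 are not among them.

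**Adequacy under the plan's own argument.** Section 11.2 cites 24 to 50 participants as adequate for a feasibility study. Both 60 and 80 exceed 50, and no formal power calculation was done, so no power figure depends on which total applies.

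**The case against.** The best defence is that this is an incomplete update, not two rival designs. The four-group design is explicit in the synopsis and in sections 5.2, 6.1, 7.1, 7.2 and 8.1. Section 8.1 also speaks of the stroke sub-group alongside a main study, so 60 in the main study plus 20 in the stroke group makes 80. That is a plausible history and it bears on severity. It does not cure the text: section 14.1 calls 60 the total, and the synopsis counts stroke inside its own total.

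Several stronger readings are tempting, and the documents do not support them.

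- *That stroke participants are left out of the outcome analysis.* The three-population list belongs to the feasibility and baseline comparison. The outcome ANOVA names no groups, and section 11.7 includes everyone randomised, so no omission is shown there.
- *That the recruitment endpoint would give two different percentages, one per total.* This needs the target total as denominator. The synopsis names none, and those approached or eligible would serve equally well. No recruitment success threshold is stated either.
- *That 60, or 80, is too few.* Nothing here shows that.
- *That other sections prove 60 means enrolled.* The no-replacement sentence in section 8.9 covers only the healthy volunteer arm, and sections 9.3 and 11.7 do not say what the 60 counts. Only the recruitment wording of section 14.1 and the drop-out margin in section 11.2 point towards enrolled. The wording needs clarifying; it is not a proven contradiction.

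**Conclusion.** The inconsistency is confirmed. The sample size in section 11.2, repeated in section 14.1, is wrong for the trial described in the synopsis: it is short by one group of 20. Section 5.1 omits that group from the primary objective, and so does the list for the baseline comparison in section 11.1.

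The practical size is 100–107 people to assess instead of 75–80, and about 8.7 months of recruitment instead of 6.5, on the plan's own window-failure and pilot rates. The sample-size argument is not weakened and no success criterion moves. This should be fixed because it concerns a stated sample size and the first primary endpoint. It does not put the design in doubt.

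**What to change.** 1. **Section 11.2:** state 80 participants in four groups of 20, naming post-ischaemic stroke, and rewrite the sentence that justifies a target of 60 so that it defends 80 against the 24–50 benchmark. Say that 20 per group counts participants enrolled and randomised. If the sponsor means completers, the text must say so and give the matching enrolment.
2. **Section 14.1, Recruitment:** give the same total and groups. Restate the recruitment-rate basis for 80 (about 8.7 months at 55 per 6 months), and say whether that rate is expected to hold for the stroke group.
3. **Section 5.1:** add post-ischaemic stroke, to match the synopsis.
4. **Section 11.1, Feasibility and Baseline Demographics:** add post-ischaemic stroke to the population list.
5. **Synopsis and section 6.2:** use one wording for the first primary endpoint, and name the denominator if it stays a percentage.

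The Background (section 4) also describes three populations and can be aligned in the same edit.

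The cost is text only. On the enrolled reading, no participants are added beyond the 80 already planned in the synopsis.

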## 11.3 The Level of Statistical Significance

Statistical significance will be set at  $p<0.05$ .

## 11.4 Criteria for the Termination of the Trial.

This is a feasibility trial, therefore trial termination will be after the final participant has completed all assessments or interview.

## 11.5 Procedure for Accounting for Missing, Unused, and Spurious Data.

Unused data will be reported, with reasons in the final report after study completion, and in any publication. Spurious and missing data will be reported, but not included in final analyses.

## 11.6 Procedures for Reporting any Deviation(s) from the Original Statistical Plan

Statistical support, including any deviations will be supported by the departmental statistician, [name]. Any deviations will be reported to the Trial Steering Committee (TSC), and included in any reports to Sponsor or REC.

#### 11.7 Inclusion in Analysis

All randomised participants will be included in the analysis.

#### Respondent Validation

The technique of showing the transcripts to the research participants and ascertaining their opinions on the accuracy of the transcripts will be used, to establish the degree of correspondence between the researcher's views and those of the research participants (36). Once completed the transcripts of the semi-structured interviews will be sent to the participants for their approval. Any comments by the participant will be added prior to analysis. This technique ensures the researchers accurately portray the experiences and viewpoints of the research participants. It is also hoped that by involving research participants in analysis and interpretation it will increase their engagement with the research.

## **12. DIRECT ACCESS TO SOURCE DATA/DOCUMENTS**

Direct access will be granted to authorised representatives from the sponsor, host institution, and the regulatory authorities to permit trial-related monitoring, audits and inspections.

### **13. QUALITY CONTROL AND QUALITY ASSURANCE PROCEDURES**

The study will be conducted in accordance with the current approved protocol, ICH GCP, relevant regulations and standard operating procedures.

The University of Leicester operate a risk based audit programme to which this study will be subject.

## **14. CODES OF PRACTICE AND REGULATIONS**

### **14.1 Ethics**

#### **Consent and Capacity**

This study plans to recruit participants with dementia or cognitive impairment. We anticipate that a number of participants will not have sufficient capacity to consent to the study. Given the nature of dementia, we feel it would be unethical to exclude participants who are unable to consent to the study, particularly where they have expressed prior willingness to be involved in research should they lose capacity. Therefore, for those individuals who do not have capacity, we plan to consent a close relative, friend or carer (personal consultee) who is able to express the views of the participant and consent on their behalf to the study. Any volunteer who has been recruited through this process who appears distressed or unwilling to participate in the study at any point will be withdrawn accordingly. Participants who have capacity will be asked at the point of consent what they would like to happen should they lose capacity, i.e. be withdrawn from the study, or continue in the study. Any participant who then loses capacity, an assessment of this pre-disclosed opinion, any available personal consultee opinion and their ongoing engagement/willingness or lack of distress will be used to decide whether study participation should continue. If there is any doubt about ongoing participation, this can be referred to the trial steering committee and/or research supervisors. Participants who lack capacity at study inclusion who later regain capacity will be re-consented before ongoing study participation.

#### **Waiting list control for intervention**

All study participants who are randomised to the control arm will be offered the intervention at the end of the study (waiting list control). This is not a cross over trial, and therefore these participants will not have any further assessments after provision of the CT program. This is to remove any ethical concerns about participants not being able to undertake the CT program through study participation. Some participants may deteriorate over the course of the study and may be unable to utilise the intervention effectively as waiting list control.

#### **Recruitment**

A broad recruitment strategy has been developed to ensure this project can recruit to target (total 60 participants, 20 healthy older adults, 20 MCI and 20 AzD). This will encompass memory and geriatric clinics, GP surgeries, and community groups. This recruitment strategy and rate has been based on a recent pilot study undertaken in the department where 55 participants were recruited over a period of 6 months.

#### Study procedures

All methods in this study have been tested in a recent pilot observational study. The TCD device utilises a head-frame which exerts a slight pressure; but has been used previously in several studies in the department and is well tolerated in patients with stroke and dementia. Participants will wear a finger blood pressure monitor, which exerts intermittent pressure. Again, this has been well tolerated in previous studies of patients with stroke and dementia.

#### Industry collaboration

This study is being undertaken as a collaboration between Lumosity© and University of Leicester. Lumosity© are providing the CT program free of charge but have not funded this study, and therefore the study is financially independent of Lumosity©. A contract has been checked by the University of Leicester who will retain the rights to publication.

#### 14.2 Sponsor Standard Operating Procedures

All relevant Sponsor SOPs will be followed to ensure that this study complies with all relevant legislation and guidelines

#### 14.3 Declaration of Helsinki

The Investigator will ensure that this study is conducted in full conformity with the current revision of the Declaration of Helsinki (last amended October 2000, with additional footnotes added 2002 and 2004).

#### 14.4 ICH Guidelines for Good Clinical Practice

The Investigator will ensure that this study is conducted in full conformity with relevant regulations and with the ICH Guidelines for Good Clinical Practice (CPMP/ICH/135/95) July 1996.

#### 14.5 Approvals

Once Sponsor authorisation has been confirmed, the protocol, informed consent form, participant information sheet and any proposed advertising material will be submitted to an appropriate Research Ethics Committee (REC), Health Research Authority (HRA), and host institution(s) for written approval.

Once Sponsor authorisation has been confirmed, the Investigator will submit and, where necessary, obtain approval from the above parties for all substantial amendments to the original approved documents.

#### 14.6 Participant Confidentiality

The trial staff will ensure that the participants' anonymity is maintained. The participants will be identified only by initials and a participants ID number on the CRF and any electronic database. All documents will be stored securely and only accessible by trial staff and authorised personnel. The study will comply with the Data Protection Act which requires data to be anonymised as soon as it is practical to do so.

#### 14.7 Other Ethical Considerations

As outlined above.

## **15. DATA HANDLING AND RECORD KEEPING**

### **15.1 Data Extraction**

As supportive evidence of the diagnosis of MCI or AzD, results and significant findings from Computerised Tomography (CTo) head/Brain Magnetic Resonance Imaging (MRI), if undertaken, will be recorded on the CRF.

Other information which will be extracted from the medical notes and recorded on the CRF include results and details of any previous cognitive testing, and the date of diagnosis of MCI or AzD.

### **15.2 Data Analysis**

All other parameters recorded, including CBFv, heart rate, blood pressure, and ETCO2 will be simultaneously recorded onto a computer system (PHYSIDAS), providing data for subsequent analyses. Off-line analyses will be undertaken using software designed by the University of Leicester's Department of Cardiovascular Sciences.

### **15.3 Data Management**

All parameters (signals) that are collected during the measurement will be saved using a coded filename. The name and other identifying detail will NOT be included in any study data electronic file. All study data will be entered into Microsoft Excel for Windows.

All files will be encrypted and stored on a password secured computer/laptop, which will have restricted access to members who are authorised on the authorisation log.

The participants will be identified by a study specific participant number and/or code in any database. The name and any other identifying detail will NOT be included in any study data electronic file.

## **16. STUDY GOVERNANCE**

### **16.1 Trial Steering Committee (TSC)**

A TSC consisting of lay members, and independent academics from the host institution, will be convened. The TSC will meet at six monthly intervals, and will assess the progress of the trial, recruitment, compliance with study protocol, ethical and regulatory standards, and safety or adverse outcomes.

### **16.2 Data Safety Monitoring Committee (DSMC)**

As this is a non-pharmacological feasibility RCT, a DSMC is not required, but adverse events will be reviewed at TSC meetings.

